9.2.2 Secondary Outcome Measures

9.2.2.1 Vd, CL/F, Ka for pregnant women in their second or third trimester.

9.2.2.2 RPT and desRPT concentrations in infants born to women receiving once-weekly RPT + INH.

9.2.2.3 Tolerability

- Permanent discontinuation of study drug regimen (i.e., RPT, INH, and pyridoxine)
- All AEs leading to permanent discontinuation of study drug regimen (i.e., RPT, INH, and pyridoxine)

9.2.2.4 RPT and des-RPT concentrations in breast milk of postpartum women receiving once-weekly RPT + INH.

9.2.2.5 Incidence of active TB in mother-infant pairs up to 24 weeks postpartum.

9.2.2.6 Estimates of CL/F, absorption, and volume of distribution of INH.

9.3 Stratification

Pregnant women will be stratified by gestational age. Cohort 1 includes pregnant women ≥ 14 weeks gestation through < 28 weeks gestation, and Cohort 2 includes pregnant women ≥ 28 weeks gestation through ≤ 34 weeks gestation. The eligibility determinations will guarantee enrollment of at least 10 HIV-1-infected women in each cohort, and the algorithm will endeavor to balance sites with respect to number of HIV-1-infected women per site.

9.4 Accrual and Participant Number

Up to 82 pregnant women will be accrued to yield 50 evaluable women (a minimum of 25 evaluable women in each cohort) and their infants. A target of at least 10 evaluable HIV-1-infected pregnant women will be enrolled in each cohort.

Women are considered evaluable if they meet any of the following criteria:

- Contribute any data to the Intensive PK or Sparse PK sampling collections
- Complete the study drug regimen (see Section 5.1.2 for adherence definition)

9.5 Sample Size Justification

9.5.1 Precision of RPT Clearance Estimation

The stochastic simulation-estimation (SSE) methodology for clinical trial simulation and re-estimation was employed to evaluate sample sizes required to evaluate key pharmacokinetic parameters with precision adequate for decision making on use of RPT + INH in pregnancy (60). This methodology simulates the data from a planned trial with proposed design (number of samples, patients), followed by the estimation of the parameters under the true and alternative model. This is repeated at least 1,000 times, and parameter estimates, relative standard error (RSE), and between subject variability (BSV) estimates are assessed. Table 3 below shows that the RSE of the estimated contrast between median clearance in second trimester and median clearance in third trimester (CL_3rd, column 3) reaches a desirable level of 18% for a total evaluable sample size of 50 women. Precision of estimation of other parameters (CL, V, ka) and BSV are seen to be very good for this sample size, and the estimation of between-participant variation achieves reasonable precision at N=50 as well. In general, RSE of 5% for a pharmacokinetic parameter (e.g. CL, V, ka), 10% for impact of covariate (e.g., impact of pregnancy on CL), and 20% for BSV is considered satisfactory. This is based on literature reviews where RSE associated with these parameters are often higher than proposed values here.

Table 3: Evaluation of sample sizes and power

Number of participants	RSE (CL) (%)	RSE, CL_3 rd (%)	RSE (V) (%)	RSE (ka) (%)	RSE (BSV-CL) (%)	RSE (BSV-V) (%)	Power (%)
10	9	39	9	12	36	41	82.2
15	8	33	8	10	33	35	91
20	7	27	7	9	29	32	94.6
30	6	23	6	7	25	27	98.2
40	5	20	5	6	22	24	99.5
50	5	18	4	6	20	22	99.9
60	4	17	4	5	18	19	100
70	4	14	4	5	17	18	100

The power for an interim analysis sample of size 12 has been computed in comparison to a fixed historical value via a likelihood ratio test at the 0.01 level. Using the stochastic simulation and estimation methodology (60) and employing all available historical data, for Type I error rate of 1%, the power to detect an average 25% departure from mean historical value of CL with 12 individuals is 96%.

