IMPAACT 2001 will be the first detailed study of the newer, shorter, and more tolerable regimen of RPT and INH with a focus on the metabolic alterations associated with pregnancy. The dose selected is the standard of care for adults based on TBTC 26 (see Section 1.2) and what is known about the metabolism of rifapentine in other populations (see Appendix II). This dose is expected to be appropriate for pregnant women as well.

The sampling strategy planned for IMPAACT 2001 is consistent with PK sampling in adults participating in TBTC trials of RPT, which will allow for comparison of the proposed IMPAACT 2001 study data with data from non-pregnant adults. Specifically, TBTC 26 used clearance as the main PK parameter, which will also be used as the primary PK parameter in IMPAACT 2001 for comparison with the non-pregnant historical controls (58). The sampling schedule is based on the expected PK profiles of RPT. The use of an intensive sampling strategy will support development of a model that estimates RPT PK well among pregnant women, including estimates for typical values and variability around absorption and elimination of the drug in this special population. The population PK modeling will be used to examine covariate effects (such as gestational age and weight) on PK parameters. With the sample size of 50 evaluable subjects, there will also be 90% power to detect one or more safety events for which the true rate of occurrence is 5 per 100 women or infants treated. The use of an interim analysis is a conservative approach, because there may be several different scenarios and variations in PK for RPT (e.g., changes in second trimester only, changes in third trimester only, similar changes in both trimesters, different changes in each trimester). With this approach, there will be power to detect all of them. To this end, a relatively large sample size is preferred to account for variability of the drug, itself, and possible physiologic differences between the second and third trimesters. Enrollment of half of each of the cohorts will provide sufficient power to detect a trimester-to-trimester effect.

The key limitations of using historical controls include the possibilities that controls and treated individuals (a) represent incomparable populations, and/or (b) differ systematically on key factors that affect the relationship between treatment and endpoint, and/or (c) encounter important differences in

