The Intensive PK sampling must be initiated on the same day (ideally in the morning) as the first dose of the study drug regimen, and conducted over the course of 72 hours according to the following time points: just prior to the first dose (t0), then 0.5h, 1h, 2h, 4h, 5h, 8h, 12h, 24h, 48h and 72h after the observed dose. Depending on site capacity, women may stay at the clinical research facility overnight after day 1 of the Entry Visit or return to the clinic at a designated time in the morning for administration of study drug and initiation of PK sampling. The same procedure can be followed for obtaining the PK samples at 48 and 72 hours after dosing.

Women will be asked to refrain from eating for two hours prior to each PK sampling dose of study drug, except for the meal provided by the site, which is to be eaten within 30 minutes before study drug administration. Women will be asked to refrain from further intake (except water) until three to four hours after the dose. The food type and quantity prior to each PK sampling dose will be recorded on CRFs.

RPT PK testing will be performed on all Intensive PK samples, after which, the t0 and 2h (or 4h) samples will be stored for later INH PK testing (see LPC for further details).

Women will be counseled about the signs and symptoms of active TB and asked to come to the clinic for an interim visit should any of the symptoms develop during the course of the study.

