Appendix II: Modeling and Simulation Population Analysis Report – Rifapentine

This population pharmacokinetic (PK) analysis estimates the pharmacokinetics of rifapentine (RPT) and its main metabolite 25-desacetyl-rifapentine (25-des-RPT) based on the combined dataset from 4 clinical studies in children, healthy adolescents and adult patients with active or latent tuberculosis infection (LTBI) where rifapentine was administered either as a single dose or weekly: two Phase I clinical studies (children, adolescents) (63, 64), one Phase I/II clinical study (TBTC Study 25) (65) and one Phase III clinical study (TBTC Study 26) (25).

The population PK analysis comprised a total of 1634 rifapentine and 25-desacetyl-rifapentine serum concentrations from 227 children, adolescents and patients with active or latent tuberculosis who received a range of 300-1200 mg oral doses of rifapentine as a single agent (children, adolescents), or in combination with isoniazid (INH) in TBTC Study 25 and TBTC Study 26. Serum concentration data of RPT and 25-des-RPT were modeled simultaneously using a population analysis approach to estimate RPT and 25-des-RPT population PK parameters (mean and inter-patient variability) as well as the relationship between PK parameters and covariates.

The structural model that best described the pharmacokinetics of rifapentine was a 1-compartment model with a transit compartment chain for description of the absorption delay. All clearance and volume of distribution parameters were allometrically scaled using standard exponents (e.g. 0.75 for clearance and 1 for volume). The following typical population estimates (%RSE) of rifapentine pharmacokinetics were obtained: oral clearance (CL/F) for 70kg patient 2.32 L/h (11 %); central volume of distribution (Vc/F) for 70 kg patient 51.7 L (10 %); absorption rate constant (k_a) 1.69 (34) h⁻¹, mean transit time (MTT) 0.62 h (27) and number of transit compartments (n) 1.8 (76). The inter-patient variability was 40% (13 %) for CL/F, 47% (15 %) for V/F and 90% (47 %) for MTT.

The structural model that best described the pharmacokinetics of 25-des-RPT was a 1-compartment model. The typical population estimates (%RSE) of 25-des-RPT apparent clearance (CL_m/F_m) and apparent volume (V_m/F_m) for 70kg patient were 2.05 L/h (10 %) and 21.9 L (7 %), respectively. The inter-patient variability was 64% (18 %) for CL_m/F_m.

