TBTC Study 26 was a Phase 3, randomized treatment trial of 8,053 patients with LTBI, comparing a 12-dose, once-weekly rifapentine and isoniazid regimen (3HP) to nine months of daily isoniazid (25). 161 patients were recruited into PK substudy from the Phase 3, PREVENT TB trial, of whom 157 had evaluable PK samples (80 children and 77 adults). Risk groups in the treatment trial were recent close contacts of pulmonary tuberculosis cases, HIV-infected persons, those with a recent tuberculin skin test conversion, or those with fibrotic or fibronodular abnormalities consistent with old, healed tuberculosis on chest radiograph. All patients had evidence of latent tuberculosis infection (e.g. positive tuberculin skin test) and no evidence of active tuberculosis. Children enrolled in this substudy were age 2 to 11 years and all children and adults in the PK substudy were treated with 3HP. Rifapentine was administered as 150 mg tablets. Rifapentine doses in children ranged from 300 to 900 mg based on weight and dosage (Table 2) and the rifapentine dose in adults was 900 mg (all patients weighed more than 45 kg). Children who could not swallow tablets were administered a suspension of crushed rifapentine and isoniazid tablets in either a soft food or liquid. Other foods consumed within two hours of drug administration were documented. For children, the once-weekly dosage of isoniazid was 25 mg/kg, (900 mg maximum), and adults were administered isoniazid 15 mg/kg (900 mg maximum) (25).

Table 2. Rifapentine dosing algorithm used for children in the PREVENT-TB study

Weight (kg)	Rifapentine dose (mg)	Rifapentine dosage (mg/kg)	Number of children in each group	Age of study patients (mean +SD in years)
10-14	300	21-30	34	2.6 \pm 0.8
>14-25	450	18-32	40	4.5 \pm 1.6
>25-32	600	19-24	7	7.4 \pm 2.2
>32-50	750	15-23	16	9.7 \pm 2.4
>50	900	<18	3	10.0 \pm 1.0

After at least three once-weekly doses of rifapentine and isoniazid, a single plasma sample collected 24-hours after administration of study drugs (C24) was used in the sampling protocol. A 2 mL venous blood sample for PK analysis was obtained 23 to 25 hours after drug administration and was processed according to standard procedures (67). Plasma concentrations of rifapentine and 25-des-RPT were determined using a validated high-pressure liquid chromatography assay (66).

Children study

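### The single 96% interim power in Protocol 9.5.1 is not supported by the documents' own variability figures, least of all for a rise in clearance, and it describes neither of the 25% interim criteria.

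*Protocol*

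**What the plan says.** Protocol 9.5.1 describes the interim calculation in two sentences. The first opens "The power for an interim analysis sample of size 12 has been computed in comparison to a fixed historical value", by a likelihood ratio test at the 0.01 level. The second says that, from simulation and estimation using the available historical data, "the power to detect an average 25% departure from mean historical value of CL with 12 individuals is 96" (per cent). No variability, residual error, direction or sidedness is given.

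Three other places bear on it:

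- **Appendix II** reports the historical model: "The inter-patient variability was 40% (13 %) for CL/F". No other CL/F variability appears in either document.
- **Table 3** (9.5.1) gives the relative standard error (RSE) of CL as 9, 8, 7 and 6% at N = 10, 15, 20 and 30, with a Power column of 82.2, 91, 94.6 and 98.2%. The hypothesis and alpha behind that column are not stated. The text says that the RSE of the trimester contrast "reaches a desirable level of 18% for a total evaluable sample size of 50 women", so N may count both cohorts.
- **Section 1.3** lists several possible patterns of change by trimester and concludes: "With this approach, there will be power to detect all of them".

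The interim decision itself uses no test. Section 10.3 opens with a comparison of median CL/F but calls the dose acceptable if median exposure is altered by no more than 25%. Section 10.3.2 puts the 25% limit on median CL/F and says that a dose adjustment will then be discussed.

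**The concern.** A reader of 9.5.1 and 1.3 will take it that a 25% change in clearance, up or down, is almost certain to be found with 12 women. Two things cast doubt on this. With 40% BSV the standard error of log CL from 12 women is about 0.115, while a 25% rise is only 0.223 on that scale, under two standard errors. And the 96% concerns rejecting equality with a fixed value, whereas the interim decision asks whether a point estimate lies beyond 25%.

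What is at stake is the assurance given to the Core Team, the Study Monitoring Committee (SMC) and ethics committees about what this look can detect. A rise carries the larger consequence: under 10.3.2 an increase leads to 25 newly enrolled evaluable women in that cohort.

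**Working it through.** **Method.** On the log scale, power = Φ(d/SE − z), with d = ln 1.25 = 0.2231 (rise) or |ln 0.75| = 0.2877 (fall), and z = 2.576 (two-sided 0.01) or 2.326 (one-sided). Assumptions: log-normal CL/F, fixed reference value, no residual error. For a given BSV these are upper limits.

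**1. Reproducing the 96%.** Its inputs are unreported, so I solved for the BSV it would need. With n = 12, two-sided, BSV = d√12/(2.576 + 1.751): 17.9% (rise) or 23.0% (fall).

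**2. Appendix II's 40%.** SE = 0.40/√12 = 0.1155.

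- Two-sided: Φ(1.932 − 2.576) = 26% (rise); Φ(2.491 − 2.576) = 47% (fall).
- One-sided: 35% and 57%.
- A simulated likelihood ratio test with the variance estimated (error-free CL/F, 400,000 replicates) gives 23% and 40%.
- Women needed for 96%, two-sided: (0.40 × 4.327/d)² = 60.2 and 36.2, so 61 and 37.

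**3. Table 3's RSE(CL), used as the SE of log CL.** If N is the interim sample, the N = 10 and N = 15 rows bracket 12. If 12 per cohort means N = 24, root-N scaling of the N = 20 row (7, rounded from 6.5–7.5) gives 5.93–6.85%, and of the N = 30 row (6, from 5.5–6.5) gives 6.15–7.27%. The overlap is 6.15–6.85%.

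| SE of log CL | Rise, two-sided | Fall, two-sided | Rise, one-sided | Fall, one-sided |
|---|---|---|---|---|
| 0.1155 (BSV 40%, n = 12) | 26% | 47% | 35% | 57% |
| 0.09 (Table 3, N = 10) | 46% | 73% | 56% | 81% |
| 0.08 (Table 3, N = 15) | 59% | 85% | 68% | 90% |
| 0.0685 (N = 24, largest) | 75% | 95% | 82% | 97% |
| 0.0615 (N = 24, smallest) | 85% | 98% | 90% | 99% |

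**4. Natural scale.**

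- *Fall, N = 12.* With the SE proportional to the reduced CL, power = Φ(0.25/(0.75 × RSE) − z). At RSE 7.8–8.2% this is about 93–98% over both sidednesses, so a fall can also reach 96% here.
- *Rise, N = 12.* With the SE set at the historical CL, the best case (RSE 7.8%, one-sided) is 81%.
- *Rise, N = 24.* Only the smallest RSE, one-sided, reaches it: Φ(0.25/0.0615 − 2.326) = Φ(1.74) = 96%.

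**5. Table 3's Power column.** Linear interpolation gives 82.2 + (2/5)(91 − 82.2) = 85.7% at N = 12 and 94.6 + (4/10)(98.2 − 94.6) = 96.0% at N = 24.

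**6. The interim criteria.** The log of the estimated CL ratio is taken as normal around the log of the true ratio, with SE = BSV/√n. The 10.3.2 rule is met if the estimated ratio is below 0.75 or above 1.25. With AUC = dose/CL, as 10.3.2 defines it, the 10.3 exposure criterion is breached if the CL ratio is above 1/0.75 = 1.333 or below 1/1.25 = 0.80. At BSV 40%, n = 12:

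| True CL change | 10.3.2 (CL/F) flags | 10.3 (exposure) flags |
|---|---|---|
| none | 3% | 3% |
| +25% | 50% | 29% |
| −25% | 50% | 71% |
| +30% | 63% | 41% |
| −30% | 73% | 88% |
| +50% | 94% | 85% |
| −40% | 97% | 99% |

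At BSV 23% the CL/F rule still flags 50% at ±25%, with 72% at +30% and 85% at −30%; the exposure criterion flags 17% at +25% and 83% at −25%. A 30% change is the size of both worked examples in 10.3.2.

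**7. Fewer Cohort 1 women.** Under 10.3.1, Cohort 2 enrolment can trigger the Cohort 1 look. For illustration, at BSV 40% the CL/F rule with 8 women flags 8% at no change, 61% at +30% and 69% at −30%.

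**The case against.** The strongest reply is that 40% is not the variability that the simulation used, and need not be. Appendix II pools children, adolescents and adults; 157 of its 227 subjects come from the study in which "a single plasma sample collected 24-hours after administration of study drugs (C24) was used in the sampling protocol". This trial samples before the dose, "then 0.5h, 1h, 2h, 4h, 5h, 8h, 12h, 24h, 48h and 72h after the observed dose". Table 3 itself implies a BSV of about 28–35% (RSE × √N), or 20–25% if N is split over two cohorts. The combined-N reading is also natural: 9.5.1 speaks of a total sample, and 1.3 says "Enrollment of half of each of the cohorts will provide sufficient power to detect a trimester-to-trimester effect". On that reading a fall gives 95–98% and the Power column interpolates to 96%.

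Much of this stands. A BSV below 40% may be defensible, and 96% is plausible for a fall. But the protocol neither states nor justifies a lower value, and the Appendix II model already adjusts for weight, maturation and food. The Power column may refer to the trimester contrast, and without its hypothesis and alpha it settles nothing. The combined-N reading still leaves a rise at 75–85% two-sided.

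A second reply is that any point-estimate cut-off is crossed about half the time when the truth lies on it, and that 9.5.1 openly describes a test. Both are true. The gap is that no operating characteristics are given for the criteria that are used.

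A reader might go further and infer that the simulation was run wrongly, or that true power is 26%. The documents do not show this, because its inputs are not reported. Nor does the 50% figure apply to both sections: it holds for the CL/F rule in 10.3.2, not for the exposure criterion in 10.3.

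**Conclusion.** The concern holds as a matter of unsupported assurance. One figure of 96% does not fit both directions on the documents' own numbers. For a 25% rise, two-sided log-scale power runs from 26% (Appendix II BSV) through 46–59% to 75–85% (Table 3, by reading of N), and 96% appears only at the extreme of favourable assumptions. For a fall, 47% at 40% BSV rises to values that include 96% on some readings of Table 3.

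Separately, the 96% does not describe the interim decision, and 10.3 and 10.3.2 apply their 25% limits to different quantities that trigger at different rates. That conclusion does not depend on the BSV, although the exact rates do.

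A reader might also infer that the dose decision will fail. The documents do not support that: crossing the limit leads to Core Team assessment, with SMC review, and not to an automatic change; large changes are usually flagged; and accrual continues afterwards. The point should be fixed; confidence is medium because the simulation inputs are hidden and the closed forms ignore residual error.

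**What to change.** - In 9.5.1, state and justify the BSV, residual error, sidedness and direction behind the 96%. Re-run at that BSV and at 40%, and replace the single figure with separate power for a 25% rise and a 25% fall.
- Say whether Table 3's N counts one cohort or both, and what hypothesis and alpha its Power column uses.
- Reconcile the exposure criterion in 10.3 with the CL/F criterion in 10.3.2. This review does not choose between them.
- Tabulate the chance of triggering the reconciled criterion for true CL ratios of 0.6 to 1.5, at n = 12 and at smaller Cohort 1 numbers.
- Qualify the claim in 1.3 that all scenarios can be detected.
- Give the Core Team and SMC the estimated CL/F ratio with a confidence interval at the interim.

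The cost is one re-run of an existing simulation, a small table, wording changes in 1.3, 9.5.1, 10.3 and 10.3.2, and a less favourable stated power. Enrolment and visits are unchanged, and no dose rule is proposed.

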9.5.2 Precision of Estimation of Adverse Events Incidence

With a sample size of 50 evaluable subjects, there is 90% power to detect one or more safety events for which the true rate of occurrence is 5 per 100 women or infants treated (see Table 4). The sample size of 25 per cohort is sufficient to rule out only very extreme safety incidence rates. For example, if zero safety events are noted for a cohort of size 25, the upper bound of a 95% confidence interval for the event rate is approximately 15%. If two events are observed for such a cohort, the upper bound is in the vicinity of 30%. Such statistics are, at best, marginally useful for decision making about the risk-benefit ratio for use of this regimen in pregnancy but should nevertheless contribute information on the tolerability and safety of the treatment. All women receiving any dose of study drug will be included in the safety analysis.

9.6 Study Monitoring: Statistical Aspects

Table 4: Power assessment for safety of protocol treatments

Cell entries are minimum sample size required to detect one or more safety events at the given rates			
	Safety Event Rates		
Power	0.05	0.1	0.15
0.8	33	17	11
0.9	47	24	16
Cell entries are minimum sample size required to detect two or more safety events at the given rates			
	Safety Event Rates		
Power	0.05	0.1	0.15
0.8	60	30	20
0.9	78	39	26

Sections 4.4 and 4.5 detail monitoring activities at the DMC concerning recruitment, enrollment, and retention. Section 7 describes procedures for safety monitoring, assessment, and reporting.

A monitoring plan will be developed for this study to ensure that the data collected are clean, complete, and of high quality and to make the team aware of the study's progress in an ongoing manner. Monthly conference calls will be held by the study team to assess study progress, and follow-up statistics will be reported to the team by the DMC on a monthly basis. Rate of enrollment will be closely monitored, with input provided from team members and participating sites on methods to speed enrollment if needed.

